2. SUMMARY OF KEY PROTOCOL INFORMATION

2.1. Changes to the Protocol Defined Statistical Analysis Plan

Any changes from the planned statistical analysis specified in the protocol amendment 2 (Dated: 26/MAY/2016) are outlined below.

- Primary and supportive analyses:
 - Protocol specified “The MMRM model via PROC MIXED will include HbA1c change from baseline at post-baseline scheduled visits up to Week 26 as dependent variables; treatment, region, age category, weight category, background antidiabetic therapy, visit week and treatment-by-week interaction; baseline HbA1c as a continuous covariate; and subject as a random effect”.
 - Changes in the Reporting & Analysis Plan:
 - Week 1 visit is excluded from the MMRM due to small or zero change in HbA1c expected at Week 1 and the primary endpoint is change from baseline in HbA1c at Week 26. Inclusion of this visit in the MMRM model does not add much statistical efficiency, instead it likely leads to a non-positive definite estimated variance matrix and thus unstable estimate of treatment effect.
 - Baseline HbA1c-by-week interaction is added in the MMRM to allow for a more appropriate model fit by accounting for different coefficients of baseline at each post-baseline visit (Week 4, 8, 12, 16, 20 and 26) and thus avoid potential convergence issue due to insufficient model specification.

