7.1.1.1. Primary Analysis on Primary Efficacy Endpoint

The primary endpoint is the change from baseline in HbA_{1c} at Week 26. The primary analysis of the primary endpoint will be conducted using a mixed-effect model with repeated measures (MMRM) in the ITT Population. The primary analysis will include all HbA_{1c} values collected at scheduled visits from Week 4 up to Week 26. This will include values after hyperglycemia rescue and discontinuation from investigational product. Imputation under the non-inferiority null hypothesis for missing data will be incorporated [Koch, 2008]. Multiple imputation assuming missing at random (MAR) will be used to replace missing data of change from baseline of HbA_{1c} at Week 26 for all subjects in both treatment arms as a first step, and then to make all the imputed values for the liquid drug product arm worse by the non-inferiority margin 0.4.

Multiple imputation approach under MAR uses separate means and variance-covariance parameter estimation for each treatment arm (Carpenter and Kenward, 2013). Missing values for each subject will be imputed multiple times based on his or her own observed HbA_{1c} change from baseline values available and also based on the estimated means and variance-covariance from the treatment group where that subject is randomized to. This approach will be used for all missing data at Week 26 due to any reason including, but not limited to lost to follow-up and withdrawal consent. The details of implementing this multiple imputation approach are the following:

- **Step 1a:** Missing values at Week 26 will be imputed 100 times via SAS PROC MI (specifying BY treatment group, using MCMC statement with the option chain = multiple, including baseline and all post-baseline scheduled visits up to Week 26). As a result, 100 imputed datasets will be generated. Note: Only imputed values at Week 26 will be retained while the imputed values at other visits will be dropped from the imputed datasets.
- **Step 1b:** For each of the 100 imputed datasets from Step 1 the imputed values at Week 26 for the liquid drug product arm will be increased by 0.4.
- **Step 2:** Apply MMRM analysis as specified below for each of the 100 imputed dataset and save LSmeans (standard error) for each treatment arm at Week 26 and difference in LSmeans between treatment groups (standard error) from each of the 100 analyses.

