- **Step 3:** Combine the 100 set of analysis results using Rubin's rules (Rubin, 1987) via SAS PROC MIANALYZE. The treatment differences, confidence intervals and p-values will be estimated by MODELEFFECTS and STDERR statement. Use the degrees of freedom (EDF) you would have if the dataset were complete.

The MMRM model via PROC MIXED will include HbA_{1c} change from baseline at post-baseline scheduled visits from Week 4 up to Week 26 as dependent variables; treatment, region (defined in [Appendix 8: Multicenter](#)), age category (<65 or ≥65 years), weight category (<90 or ≥90 kg), background antidiabetic therapy (diet and exercise or stable dose of metformin), visit week, treatment-by-week interaction and baseline HbA_{1c}-by-week interaction as fixed effects; baseline HbA_{1c} as a continuous covariate; and subject as a random effect. An unstructured covariance matrix will be used for the MMRM analysis, unless the model does not converge, in which case the covariance matrix will be decided upon model convergence status and the Akaike information criterion. Treatment effects estimates (and associated CI) of albiglutide liquid drug product will be evaluated within this MMRM model as least squares means contrasts relative to the lyophilized drug product.

The null hypothesis will be tested based on the 1-sided 97.5% confidence interval (with upper bound, equal to that of 2-sided 95% confidence interval) of the treatment difference at Week 26, which is estimated from the multiple imputation/MMRM (i.e. combined MMRM results from multiple imputation). If the upper bound of the confidence interval is less than or equal to 0.4%, non-inferiority will be concluded.

In addition, the observed HbA_{1c} and change from baseline HbA_{1c} will be summarized descriptively and presented graphically.

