11.9. Appendix 9: Examination of Covariates, Subgroups & Other Strata

11.9.1. Strata and Covariates

The randomization for this study is stratified by the following baseline characteristics:

- Age at randomization (<65 years versus \geq 65 years)
- Weight at Screening (<90 or \geq 90 kg)
- Background antidiabetic therapy (diet and exercise or stable dose of metformin)

The primary analysis of HbA_{1c} change from baseline will use a mixed-effect model with repeated measures (MMRM), which includes HbA_{1c} change from baseline at all post-baseline visits as dependent variables; treatment, region, age category, weight category, background antidiabetic therapy, visit week, treatment-by-visit interaction as fixed effects; baseline HbA_{1c} as a continuous covariate; and subject as a random effect.

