11.11. Appendix 11: Model Checking and Diagnostics for Statistical Analyses

11.11.1. Model Checking and Diagnostics for Statistical Analyses

1. Example SAS code for the primary efficacy analysis with imputation

Step 1a: Transpose the data horizontally and then impute data assuming missing at random (EFFIM)

```
PROC MI DATA= EFF OUT= EFFIM NIMPUTE=100 SEED=4408572;
  BY TRT01PN;
  MCMC CHAIN=multiple;
  VAR BASE CHG_W1 CHG_W4 CHG_W8 CHG_W12 CHG_W16 CHG_W20 CHG_W26;
  RUN;
```

Note: need to remove all imputed values before Week 26 and retain imputed values at Week 26 only.

Step 1b: Add 0.4 to the imputed value at Week 26 in the liquid product arm and transpose data in vertical structure (EFFIM2)

Step 2: Exclude HbA1c change from baseline at Week 1 and perform MMRM for each imputed dataset

```
Ods output SLICES=SLICE LSM SLICEDIFFS=SLICEDIFF;
```

```
PROC MIXED DATA= EFFIM ;
  BY _imputation_;
  CLASS USUBJID REGION WGTGR1 AGEGR1 PRIORDTX TRT01PN AVISITN;
  MODEL CHG= BASE REGION WGTGR1 AGEGR1 PRIORDTX TRT01PN AVISITN
  TRT01PN*AVISITN BASE*AVISITN/ DDFM=KR;
  REPEATED AVISITN/SUB=USUBJID TYPE=UN;
  SLICE TRT01PN*AVISITN/sliceby(AVISITN='26') means pdiff cl cov;
  RUN;
```

Step 3: Combine results using PROC MIANALYZE

```
PROC SORT DATA=SLICE LSM; BY TRT01PN IMPUTATION; RUN;
PROC MIANALYZE DATA=SLICE LSM EDF=CDF*;
BY TRT01PN;
MODELEFFECTS ESTIMATE;
STDERR STDERR;
RUN;
```

```
PROC MIANALYZE DATA=SLICEDIFF;
MODELEFFECTS ESTIMATE;
STDERR STDERR;
RUN;
```

*CDF=complete-data degrees of freedom. This is used to calculate the adjusted degrees of freedom for the combined results.

2. Example SAS code for the by-subgroup analysis of the primary endpoint with imputation

Follow the same steps as for the example SAS code for the primary analysis except in the step 2 additional interaction terms need to be added.

Subgroup variable: Baseline HbA1c <8% or >=8%

```
ods output SLICES=SLICELSM1 SLICEDIFFS=SLICEDIFF1;
PROC MIXED DATA= EFFIM;
  BY imputation;
  CLASS USUBJID REGION WGTGR1 AGEGR1 PRIORDTX TRT01PN AVISITN HBGR1;
  MODEL CHG= HBGR1 REGION WGTGR1 AGEGR1 PRIORDTX TRT01PN AVISITN
TRT01PN*AVISITN HBGR1*TRT01PN HBGR1*AVISITN
          HBGR1*TRT01PN*AVISITN/ DDFM=KR;
  REPEATED AVISITN/SUB=USUBJID TYPE=UN;
  SLICE HBGR1*TRT01PN*AVISITN/sliceby(AVISITN='26') means pdiff cl
cov;
RUN;
```

Subgroup variable: Baseline Weight <90 or >=90 kg

```
ods output SLICES=SLICELSM2 SLICEDIFFS=SLICEDIFF2;
PROC MIXED DATA= EFFIM;
  BY imputation;

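### The SAP's example code for the primary test reads the imputed dataset without the 0.4 penalty

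*SAP*

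**What the plan says.** **Text of the primary analysis.** SAP 7.1.1.1 sets out the steps. Week 26 is imputed 100 times by arm under missing at random (MAR), and then "the imputed values at Week 26 for the liquid drug product arm will be increased by 0.4". The MMRM is fitted to each completed dataset and the results are pooled by Rubin's rules. On the pooling it adds: "Use the degrees of freedom (EDF) you would have if the dataset were complete". SAP 7.1.2 repeats the 0.4 step.

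**Example code, SAP 11.11.1.**
- Step 1a writes the MAR imputation to `EFFIM`. This set is horizontal, with one column per visit: "VAR BASE CHG_W1 CHG_W4 CHG_W8 CHG_W12 CHG_W16 CHG_W20 CHG_W26".
- Step 1b creates the penalized, vertical set: "Step 1b: Add 0.4 to the imputed value at Week 26 in the liquid product arm and transpose data in vertical structure (EFFIM2".
- Step 2 fits the MMRM with "PROC MIXED DATA= EFFIM". The two subgroup programs name the same dataset.
- Step 3 pools the arm means with `EDF=CDF`. It pools the treatment difference with "PROC MIANALYZE DATA=SLICEDIFF" and no EDF option.

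**Model description.** SAP 2.1 records two departures from the protocol: "Week 1 visit is excluded from the MMRM", and a baseline HbA1c-by-week term is added. SAP 7.1.1.1, 7.1.2 and the code follow both. SAP 11.9.1 still describes the primary model with HbA1c change "at all post-baseline visits as dependent variables; treatment, region, age category, weight category, background antidiabetic therapy, visit week, treatment-by-visit interaction" and without the baseline-by-week term.

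**The concern.** The 0.4 penalty is what makes this an imputation under the non-inferiority null. Without it, the primary result becomes an MAR analysis nearly identical to Supportive Analysis 1 (Table 2.3), but reported as the primary Table 2.1.

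The code in 11.11.1 is the only code the SAP gives for the confirmatory test. It fixes the seed, the number of imputations and the variable names, and 7.1.2 sends the reader to it, so it is written to be followed.

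A literal run would probably stop with an error, because `EFFIM` as written has no `CHG` or `AVISITN`. That is limited protection. An easy repair is to transpose the dataset that the call names, which gives plausible output with no penalty in it.

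The EDF omission affects the one pooled quantity that decides non-inferiority. The 11.9.1 sentence leaves two descriptions of the primary model in one document.

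**Working it through.** **Inputs.** From SAP 11.12.1: 150 randomized per arm, SD 1, margin 0.4, one-sided alpha 0.025, 13% withdrawn or lost. From 7.1.1.1: 100 imputations. Assumed here: missing fractions f of 5% and 20% to bracket 13%, and equal missingness in both arms.

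**The plan's own figure.** With 133 per arm, SD 1 and margin 0.4, the noncentral t gives 90.15% power, so the stated 90% reproduces. Sample size is not in dispute.

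**Which dataset carries the penalty.**

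| Step in 11.11.1 | Dataset | Layout | 0.4 added |
|---|---|---|---|
| 1a, imputation | writes `EFFIM` | horizontal | no |
| 1b | writes `EFFIM2` | vertical | yes |
| 2, primary MMRM | reads `EFFIM` | needs vertical | no |
| Two subgroup MMRMs | read `EFFIM` | need vertical | no |

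**Shift if the penalty is lost.** Shift = 0.4 × f, in favour of the liquid product.

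**Type I error if the penalty is lost.** Take a true difference of 0.4, with missing liquid values 0.4 worse than MAR. The unpenalized estimate then centres on 0.4 − 0.4f, so

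type I error = Φ(0.4f/SE − 1.96), with SE = √(2/(150(1 − f))).

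| f | Shift | SE | Type I error | Simulated, no penalty | 
|---|---|---|---|---|
| 5% | 0.020 | 0.1185 | 3.7% | 3.4–4.0% |
| 13% | 0.052 | 0.1238 | 6.2% | 6.3–6.5% |
| 20% | 0.080 | 0.1291 | 9.0% | 8.9–9.4% |

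The simulation used 12,000 trials per cell, 150 per arm and arm-specific multiple imputation (40 imputations) from one earlier visit. The assumed correlation of that visit with Week 26 was 0, 0.5 or 0.8. It compared Week 26 means under Rubin's rules, not the full MMRM. With the penalty the error was 2.3–2.8%.

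**If the data are MAR.** At 13% missing and a true difference of 0.4, the rejection rate is 2.5% without the penalty and about 0.9% with it (2.65% and 0.6% in a separate simulation of 4,000 trials with 100 imputations and missing completely at random). At a true difference of 0, power is 89.6% without it and 80.0% with it (88.7% and 79.7% simulated).

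**EDF.** Assume a relative variance increase of 0.1 and complete-data df of 290. Without EDF, df = 99 × (1 + 1/0.1)² = 11,979 and t = 1.9602. With EDF, the Barnard–Rubin df is 256 and t = 1.9693. At SE 0.12 the upper bound differs by 0.12 × (1.9693 − 1.9602) = 0.0011. For variance increases of 0.05 to 0.2 and df of 250 to 290, the range is 0.0010 to 0.0014.

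**SAP 11.9.1.** The numerical effect of the older model cannot be computed from the documents.

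**The case against.** The intended analysis is not in doubt. The 0.4 step appears in the synopsis, in Sections 5, 7.1.1.1 and 7.1.2, and in Step 1b of the code itself. The code is labelled as an example and leaves several data steps as words. The harm needs a programmer to meet an error and then overlook the line just above that names the penalized set.

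The error rates also rest on an extreme scenario. If missingness is otherwise unrelated to outcome, a true difference of 0.4 with missing liquid values 0.4 worse than MAR puts missing liquid subjects 0.8 − 0.4f above the lyophilized arm. That is 0.78, 0.75 and 0.72 at 5%, 13% and 20%, close to the whole historical effect M1 of 0.75. The SAP expects similar missing-data patterns in the two arms. The nine-scenario sensitivity analysis (Table 2.19) does not use this code and would still be available.

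Most of this stands as a limit on weight. The text governs, the error rates are conditional and not an expected cost, and the EDF effect is negligible. It does not remove the defect: the only code for the confirmatory test names the wrong dataset, and the wrong repair would produce a result that looks valid.

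**Conclusion.** The concern holds. As written, SAP 11.11.1 contradicts 7.1.1.1 on the dataset for the primary test and for both subgroup programs. It also omits the required EDF for the treatment difference, and 11.9.1 describes a superseded model. Severity is minor to moderate, because the text is correct.

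The general consequence of losing the penalty is a shift of 0.4 times the liquid-arm missing fraction: 0.052 at 13%, and 0.020 to 0.080 over an assumed 5% to 20%. The type I error of 3.7% to 9.0% applies only if missing liquid values are 0.4 worse than MAR. Under MAR there is no inflation. At 13% missing and no true difference, the choice of dataset moves power by about 10 points, enough to decide a borderline result.

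**What to change.** - In SAP 11.11.1, read `EFFIM2`, sorted by `_imputation_`, in the Step 2 PROC MIXED call and in both subgroup PROC MIXED calls.
- Add `EDF=CDF` to the PROC MIANALYZE call on `SLICEDIFF`.
- In SAP 11.9.1, replace the model sentence with the 7.1.1.1 model: Weeks 4 to 26, with the baseline HbA1c-by-week term.
- Add a programming check. The liquid-minus-lyophilized difference in Table 2.1 should exceed that in Table 2.3 by about 0.4 times the observed liquid-arm Week 26 missing fraction. Near equality despite missing liquid values would show that the penalty was lost. If few values are missing, the expected gap is small and must be read against the actual count.

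The cost is a few words in the SAP before unblinding. No new data or analysis is needed.

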
 Same MMRM model as for the primary analysis
By-Subgroup Statistical Analysis

 The subgroup analyses will be performed using the same multiple imputation/MMRM model approach except in the MMRM step a treatment by subgroup interaction term is added to the model. The subgroups include baseline HbA_{1c} category, region, age category (<65 or ≥65 years), weight category (<90 or ≥90 kg), background antidiabetic therapy (diet and exercise or stable dose of metformin), gender, race, ethnicity and duration of diabetes category. Refer to Appendix 9: Examination of Covariates, Subgroups & Other Strata.

Model Specification

• Change from Baseline in HbA_{1c} = Baseline HbA_{1c} + Treatment + Region + Age Category + Weight Category + Background Antidiabetic Therapy + Visit Week + Treatment-by-Visit + Baseline HbA_{1c}-by-Visit Interaction + Subgroup (if not already in the model) + Subgroup-by-Treatment+ Subgroup-by-Visit + Subgroup-by-Treatment-by-Visit.• Refer to Appendix 11: Model Checking and Diagnostics for Statistical Analyses for SAS code
Sensitivity Statistical Analysis

• Refer to Appendix 6 Section 11.6.3.4: Sensitivity Analysis Under Missing Not At Random (MNAR)

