  CLASS USUBJID REGION WGTGR1 AGEGR1 PRIORDTX TRT01PN AVISITN;
  MODEL CHG= BASE REGION WGTGR1 AGEGR1 PRIORDTX TRT01PN AVISITN
TRT01PN*AVISITN BASE*AVISITN WGTGR1*TRT01PN WGTGR1*AVISITN
          WGTGR1*TRT01PN*AVISITN/ DDFM=KR;
  REPEATED AVISITN/SUB=USUBJID TYPE=UN;
  SLICE WGTGR1*TRT01PN*AVISITN/sliceby(AVISITN='26') means pdiff cl
cov;
RUN;
```

3. Example SAS code for the secondary efficacy analyses using MMRM without imputation

```
PROC MIXED DATA= INDATA ;
  CLASS USUBJID REGION WGTGR1 AGEGR1 PRIORDTX TRT01PN AVISITN;
  MODEL CHG= BASE REGION WGTGR1 AGEGR1 PRIORDTX TRT01PN AVISITN
TRT01PN*AVISITN BASE*AVISITN/ DDFM=KR;
  REPEATED AVISITN/SUB=USUBJID TYPE=UN;
  SLICE TRT01PN*AVISITN/slice=AVISITN means pdiff cl cov;
RUN;
```

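### The example program for the baseline-HbA1c subgroup drops the continuous baseline terms that SAP 7.1.2 keeps, and the pooling step to be reused does not isolate the treatment difference within each subgroup level

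*SAP*

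**What the plan says.** **Model in the text.** The subgroup model in SAP 7.1.2 begins "Change from Baseline in HbA_{1c} = Baseline HbA_{1c} + Treatment + Region + Age Category + Weight Category". It continues through the baseline-by-visit interaction and then appends "Subgroup (if not already in the model) + Subgroup-by-Treatment+ Subgroup-by-Visit + Subgroup-by-Treatment-by-Visit". SAP 7.1.1.3 agrees: the primary approach is used, with the interactions included as well. It asks for an adjusted treatment difference and 95% confidence interval at each level of the subgroup.

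**Model in the example code (SAP 11.11.1).** The instruction for the subgroup analysis reads: "same steps as for the example SAS code for the primary analysis except in the step 2 additional interaction terms need to be added". Two subgroup programs are printed.
- Baseline HbA1c: "MODEL CHG= HBGR1 REGION WGTGR1 AGEGR1 PRIORDTX TRT01PN AVISITN", followed by "TRT01PN*AVISITN HBGR1*TRT01PN HBGR1*AVISITN" and the three-way term. Neither `BASE` nor `BASE*AVISITN` appears.
- Weight: "MODEL CHG= BASE REGION WGTGR1 AGEGR1 PRIORDTX TRT01PN AVISITN", with `BASE*AVISITN` among the interactions.

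**Slicing and pooling.** Both programs request pairwise differences of the subgroup-by-treatment-by-visit means, sliced at Week 26 by visit only. Step 3 of the primary program runs `PROC MIANALYZE` on the differences dataset without a `BY` statement, and on the least squares means `BY` treatment only. No Step 3 is printed for the subgroups.

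**Input dataset.** Step 1b names the dataset with the +0.4 shift `EFFIM2`. The primary Step 2 and both subgroup programs read `EFFIM`.

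**The concern.** The text and the instruction above the code both say that terms are added to the primary model. The baseline-HbA1c program replaces terms instead, and nothing in the SAP explains the replacement. The plan therefore specifies two different models for Table 2.9, and which one is fitted depends on the section the programmer follows. A covariate choice of this kind should be settled before unblinding.

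The pooling gap concerns the step after the model. Step 3 suits the primary analysis, where each imputation supplies one Week 26 difference. A subgroup slice supplies several, and most of them are not treatment effects within a level. If they were pooled together, the result would not be the quantity SAP 7.1.1.3 asks for. The same gap would arise for each of Tables 2.9 to 2.17.

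**Working it through.** The plan gives no figure of its own on this point. The check compares model terms, counts contrasts, and then sizes each effect.

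**1. Terms.**

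| Term | SAP 7.1.2 text | HbA1c-subgroup code | Weight-subgroup code |
|---|---|---|---|
| `BASE` | yes | no | yes |
| `BASE*AVISITN` | yes | no | yes |
| Subgroup and its interactions | added | present | present |

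`BASE` and its two-level category are not fully aliased, so both can be fitted together.

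**2. Cost of using the category alone.** Assumptions, none from the documents: slope b of change on baseline between -0.3 and -0.7, baseline SD 0.85, total SD 1.0, and normal baseline values split at their mean. The SAP cut is 8%, and no mean baseline is given. The calculation treats Week 26 as a single cross-section.
- Variance explained by baseline: E = b² × 0.85².
- Residual variance with `BASE`: 1 - E.
- A split at the mean leaves 1 - 2/π = 0.363 of E unexplained.
- SE ratio = √[(1 - E + 0.363E) / (1 - E)].

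| b | E | 1 - E | 0.363E | SE ratio |
|---|---|---|---|---|
| -0.3 | 0.065 | 0.935 | 0.024 | 1.013 |
| -0.5 | 0.181 | 0.819 | 0.066 | 1.039 |
| -0.7 | 0.354 | 0.646 | 0.129 | 1.095 |

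**3. Contrasts per imputation.** A subgroup with L levels has 2L cells at Week 26 and C(2L, 2) pairwise differences, of which L are same-level treatment differences.

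| L | Cells | Differences | Wanted | Rows over 100 imputations |
|---|---|---|---|---|
| 2 (as in the two printed programs) | 4 | 6 | 2 | 600 |
| 3 (diabetes duration) | 6 | 15 | 3 | 1,500 |
| 4 (region) | 8 | 28 | 4 | 2,800 |

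The last two rows extend the printed pattern to programs that are not printed.

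**4. What unadapted pooling would estimate.** Take two levels, no interaction, treatment effect t and between-level difference d. The average of the six differences weights the four cells, in order, by 1/2, 1/6, -1/6 and -1/2.
- Cells ordered subgroup first: t × (1/2 - 1/6) + d × (1/2 + 1/6) = t/3 + 2d/3.
- Cells ordered treatment first: 2t/3 + d/3.

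Illustration, with assumed t = 0, SD 1 and 75 subjects per cell (150 per arm split equally): the SE of one within-level difference is √(2/75) = 0.163. With d = 0.3 the pooled value is about 0.20 or 0.10, depending on the order. With d = 0.6 it is about 0.40 or 0.20. A simulation of Rubin's rules, with small between-imputation noise (SD 0.03 per cell mean), gave pooled SEs from 0.22 to 0.48 over these cases, because the spread between contrasts is counted as between-imputation variance.

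The least squares means step, run `BY` treatment only, would likewise merge the subgroup levels within each arm.

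**The case against.** The code is labelled as an example and contains a placeholder for the degrees of freedom, so it is a template. Replacing a continuous covariate by its own category, when that category is the subgroup, is a recognisable modelling choice, and one sentence in SAP 7.1.2 could authorise it. That is fair, but no such sentence exists, and the text and instruction as written require the continuous terms.

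Three stronger readings are tempting, and the documents do not support them.

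- **That the subgroup programs, run as written, return one meaningless pooled number.** No subgroup `PROC MIANALYZE` call is printed. The subgroup programs write to `SLICEDIFF1` and `SLICEDIFF2`, whereas Step 3 reads `SLICEDIFF`, so a programmer must adapt it. SAP 7.1.1.3 already requires one difference per level, and a single number could not fill the by-subgroup tables. What stands is that the instruction to reuse Step 3 supplies neither the row selection nor the `BY` statement that the adaptation needs.
- **That the baseline-HbA1c subgroup loses adjustment for the strongest covariate.** The documents do not rank covariates by strength. Adjustment is coarsened: the category and its visit interaction remain, and under the assumptions above they capture about 64% of the variance that baseline explains.
- **That the primary conclusion is at risk.** It rests on the overall Week 26 confidence bound (SAP 7.1.1.1). No subgroup success rule is stated, and multiplicity is marked as not applicable (SAP 11.10.1).

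The `EFFIM` reference is not peculiar to the subgroup programs. The primary Step 2 has the same slip, so correcting only the subgroup code would put the two printed programs out of step.

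**Conclusion.** The contradiction between text and code is real and limited to the baseline-HbA1c subgroup; the other printed program, for weight, matches the text. Its likely cost is a standard error about 1% to 10% larger, given the assumed slopes, SDs and split at the mean. The contradiction itself does not depend on those values.

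The pooling gap is real as an incomplete instruction. The visit-only slice produces more differences than the estimand calls for, and the step to be reused does not select among them. The harm arises only if Step 3 is carried over without adaptation.

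Both are minor points of specification, worth correcting because the correction is nearly free.

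**What to change.** - In the baseline-HbA1c subgroup program, restore `BASE` and `BASE*AVISITN` alongside `HBGR1` and its interactions, so that it matches SAP 7.1.2.
- Slice by visit and subgroup level, or keep only the same-level liquid-minus-lyophilized differences. Print the subgroup pooling step with `PROC MIANALYZE` run `BY` subgroup level, and pool the least squares means by treatment and subgroup level.
- Have both the primary and the subgroup Step 2 programs read `EFFIM2`, so that all of them use the data with the +0.4 step.

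The cost is a few lines of example code. No new data are needed and nothing in the conduct of the trial changes.
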